KPS - Karnofsky Performance Status
PSCC – patient satisfaction with cancer care scale
CAT – communication assessment tool

Study Summary

Title	TELEPORT Study: A Pilot Feasibility Trial Examining The Use of Telehealth in Post Radiation Therapy Visits
Short Title	TELEPORT Study: Telehealth in Radiation Oncology
Protocol Number	15D.580
Phase	single arm pilot study
Methodology/Study Design	Any malignancy or benign condition treated with radiation single arm feasibility study
Study Duration	24 months for enrollment; 32 months for study duration
Study Center(s)	Single-center
Objectives	
Primary objective:
 
 - to investigate the feasibility of conducting a future phase 2 randomized study comparing telehealth and in person visits for patients returning for a post-radiation treatment visit 
Secondary objectives:
 
 - To examine patient satisfaction with a telehealth visit - To examine patient assessment of physician communication during a telehealth - To examine patient distrust in the healthcare system following a telehealth visit - To examine physician ability to perform a patient assessment during a telehealth visit - To examine physician perceptions of telehealth visits - To examine monetary and time cost to patients for telehealth visits - To calculate clinic savings derived from telehealth visits
Number of Subjects	65
Diagnosis and Main Inclusion Criteria	Patients receiving RT for any indication
Study Therapy,	Telehealth visit for the first post treatment follow up

Dose, Route, Regimen	
Duration of administration and follow-up	Follow up visit 3-8 weeks after completion of radiation treatment
Reference therapy	Standard in person office visit for first post treatment follow up
Statistical Methodology	

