4.0 SUBJECT SELECTION AND WITHDRAWAL

4.1 Inclusion Criteria

1. Patients who underwent, currently undergoing or planned to start radiation treatment with curative, adjuvant or palliative intent, who have not yet had their first post-treatment visit
2. Age ≥ 18
3. KPS score ≥ 60
4. Patients must be capable to read and speak English and provide study specific informed consent prior to study entry
5. Patients must have access to a computer or smartphone, email and internet connection at home or at a location convenient to them on which they would be willing to do a telehealth study
6. Pennsylvania or New Jersey residents*

*Telehealth visits for New Jersey residents will only be performed by physicians with a current medical license issued by the state of New Jersey.

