6.0 STUDY PROCEDURES

6.1 Study Visit Schedule

Screening:

Potential candidates for the study will be identified by their treating radiation oncologist. Eligibility of patients will be verified based on eligibility criteria (section 4.1). Those eligible patients will receive detailed information about the study. Patients will be informed of possible risk and benefits. Informed consent will be obtained from patients. Demographics and patient KPS will be assessed at the time of the screening visit

Visit 1:

Patients will undergo their first post-treatment visit as a virtual telehealth visit. Following the visit the treating physician will fill out the physician questionnaires on paper or online, while patients will be emailed a patient-specific link to a survey. Physicians will have 2 weeks following the date of the visit to complete the survey. Patients will have up to 4 weeks after the visit to complete the survey. Patients will receive weekly reminder emails regarding the survey up to 3 times after the visit. Patients will also have the option to fill out a paper survey (provided at the time of treatment discharge with the discharge instructions) and mail it into the office.

Follow-up

There will be no subsequent follow up

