6.1.1 Study Flowchart

	Screening visit	Post-treatment visit	Sent to patient following visit
Informed consent	X		
Background information	X		
KPS	X		
Patient Satisfaction with Cancer Care Scale ^b			X
Communication assessment tool ^b			X
Health care system distrust tool ^b			X
Physician questionnaire ^a		X	
Modified physician satisfaction scale ^a		X	

- a. Physicians are to complete surveys and satisfaction scale within 2 weeks following the visit.
- b. Patients are to complete surveys within 4 weeks following the visit. They will be emailed reminders weekly following the visit.

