In addition to meeting inclusion criteria, patients are ineligible for enrollment if any of the following exclusion criteria are met.

- Patients under the age of 18
- KPS <60%
- No access to a computer, smartphone or internet
- Unable to read and/or speak English
- Decisionally impaired patients
- Patients not residing in Pennsylvania or New Jersey

Checklist for Screening Visit:

Informed Consent for Trial Obtained	
All Sections of CRF Completed	
Inclusion/Exclusion Criteria Evaluated	
Based on screening patient appears eligible	

TELEPORT Study Case Report Form (CRF)—Follow up Visit
Patient Satisfaction with Cancer Care Scale (PSCC)

Below is a list of statements regarding your recent post-treatment visit. Please indicate your response

	Strongly agree (1)	Agree (2)	Neutral (3)	Disagree (4)	Strongly disagree (5)
I felt my concerns were understood					
I felt I was treated with courtesy and respect					
I felt included in decisions about my health					
I was told how to take care of myself					
I felt encourages to talk about my personal health concerns					
I felt I had enough time with my doctor					
My questions were answered to my satisfaction					
Making an appointment was easy					
I knew what the next step in my care would be					
I feel confident in how I deal with the health care system					
I was able to get the advice I needed about my health issues					
I knew who to contact when I had a question					
I received all the services I needed					
I am satisfied with the care I received					
The doctors seemed to communicate well about my care					
I received high quality care from my regular doctor					
I received high quality care from my specialists					
My regular doctor was informed about the results of the tests I got					

Communication assessment tool (CAT)

Please use this scale to rate the way the doctor communicated with you.

	Poor (1)	Fair (2)	Good (3)	Very good (4)	Excellent (5)
Greeted me in a way that made me feel comfortable					
Treated me with respect					
Showed interest in my ideas about my health					
Understood my main health concerns					
Paid attention to me(looked at me, listened carefully)					
Let me talk without interruptions					
Gave me as much information as I wanted					
Talked in terms I could understand					
Checked to be sure I understood everything					
Encouraged me to ask questions					
Involved me in decisions as much as I wanted					
Discussed next steps, including any follow up plans					

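### The optional paper survey is issued before the telehealth visit it rates and carries no dates, so a form completed early but mailed after the visit could enter the secondary averages undetected.

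*Combined protocol and SAP*

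**What the plan says.** Section 6.1 describes two routes for the patient survey. The main route is electronic and opens only after the visit, when each patient receives an individual link by email. The second is optional paper, returned by mail: "Patients will also have the option to fill out a paper survey (provided at the time of treatment discharge with the discharge instructions". The Study Summary gives the timing of the visit as "Follow up visit 3-8 weeks after completion of radiation treatment".

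The intended completion period lies after the visit. Section 6.1 says "Patients will have up to 4 weeks after the visit to complete the survey", and footnote b of the flowchart in 6.1.1 says "Patients are to complete surveys within 4 weeks following the visit". The flowchart column for the three patient scales is headed "Sent to patient following visit".

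In Appendix II the PSCC opens with "Below is a list of statements regarding your recent post-treatment visit". The CAT asks how the doctor communicated, without naming a visit. The distrust scale asks about the health care system in general. The screening form has a line for its date; the follow-up forms, as printed, have no line for the visit date or the completion date. Section 7.2 tests the mean satisfaction score and estimates the other averages. Section 7.3 analyses every enrolled subject. Neither says what to do with a survey completed at the wrong time.

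**The concern.** An instrument meant to rate one encounter should not be open for completion before that encounter unless the completion date is known. Here the email route is safe by construction and the paper route is not. A patient who receives the form with the discharge papers, just after a course of in-person care, can answer the CAT and the distrust scale on the spot, because neither refers to the telehealth visit. If the form is mailed after the visit, nothing on it shows that it was completed earlier.

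The secondary objectives are at stake: satisfaction, communication and distrust following a telehealth visit. Early CAT or PSCC answers would describe in-person care. Early distrust answers would not be a misdirected rating of a visit, but they would not be post-visit measurements either. A patient who never attends the visit (non-compliant under section 5.6) also holds the form, and nothing in 7.2 or 7.3 keeps that patient's survey out of the averages.

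**Working it through.** **Timing, side by side**

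| Item | Source | Timing relative to the visit |
|---|---|---|
| Paper survey issued | 6.1 | about 3-8 weeks before |
| Emailed link issued | 6.1 | after |
| Patient scales | 6.1.1, column heading | sent after |
| Completion | 6.1; 6.1.1, footnote b | up to 4 weeks after |

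The first row takes treatment discharge to be the end of radiation. That row cannot be squared with the third. Section 3.1 also asks for completion within a week rather than 4 weeks, so the limit that a date check would apply is itself unsettled.

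**What can be detected**

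- Form arrives before the visit: can be noticed, because the visit date is scheduled, although the protocol does not ask for receipt to be logged.
- Form completed early, mailed after the visit: cannot be told apart from a valid form.
- Form completed more than 4 weeks after the visit: cannot be established from the form itself.

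**The plan's own figure**

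Inputs from 7.1: n = 60, null 80%, true mean 90%, SD 5%, one-sample t-test, alpha 0.05.

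- Noncentrality = (90 − 80)/5 × √60 = 15.5.
- Power from the noncentral t distribution is above 0.999, one- or two-sided, which agrees with the stated figure of more than 90%.

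The issue is therefore possible bias, not power.

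**Size of a possible shift**

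Let f be the share of analysed surveys completed before the visit, and b the difference in their PSCC score in points. The shift in the mean is f × b. The documents give neither value, so both are assumed. The standard error under the plan's inputs is 5/√60 = 0.65 points, and the 95% half-width is about 2.0 × 0.65 = 1.3 points.

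| f | b | Shift (points) | Shift / 0.65 |
|---|---|---|---|
| 5% | 5 | 0.25 | 0.4 |
| 5% | 10 | 0.5 | 0.8 |
| 10% | 10 | 1 | 1.5 |
| 20% | 10 | 2 | 3.1 |
| 30% | 20 | 6 | 9.2 |

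The share f cannot exceed the share of surveys returned on paper.

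The planned distance from the null is 90 − 80 = 10 points (7.1), or 90 − 75 = 15 points (7.2). A downward shift of 2 points leaves 8 or 13. In the last row 4 points remain against the null of 80. Allowing for the extra spread of a mixture, the variance is 25 + 0.3 × 0.7 × 20² = 109, so the standard error is √109/√60 = 1.35. The expected t is then about 4/1.35 = 3.0, still above the two-sided critical value of about 2.0.

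**The case against.** The strongest reply is that the plan puts completion after the visit in both 6.1 and 6.1.1, and that the PSCC, which opens the patient survey, tells the patient that it concerns a recent post-treatment visit. An early form would be a protocol deviation, not an accepted rating. A form arriving before a scheduled visit can be spotted. Paper is only an option, and section 4.1 requires every participant to have email and internet access, so paper use may be low. The outcomes are secondary in a single-arm pilot.

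Most of this stands, and it limits the point. A reader might infer that early surveys would be counted as telehealth ratings, or that no premature form could ever be recognised. The documents support neither. They support only that a form completed early and mailed later could be counted without anyone knowing. Nor do they suggest that this is common.

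A reader might also note that the form is in the patient's hands for 21-56 days before the visit and 28 days after it, so that 21/49 = 43% to 56/84 = 67% of that time precedes the visit. This is a ratio of elapsed time. It says nothing about how many patients complete the form early.

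The reply does not remove the conflict between 6.1 and the flowchart, the missing dates, or the lack of a rule. The PSCC introduction is a partial safeguard only; the CAT and the distrust scale carry no such cue.

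**Conclusion.** The point holds in a limited form. The paper survey is issued before the visit it rates, against the flowchart, and the printed follow-up forms cannot show whether it was completed before or after. Mistimed answers could enter the PSCC, CAT and distrust averages undetected, and the 4-week limit cannot be verified on paper.

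Only the paper subset, of unknown size, is exposed. With an assumed 10-point difference and 5-20% early forms, the mean PSCC moves 0.5-2 points, in a direction that the documents do not settle. At the upper end this exceeds the 95% half-width of about 1.3 points, so the estimate could mislead.

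It would be going too far to say that the satisfaction test is compromised. If the true mean is near the planned 90, shifts of this size do not reverse a conclusion planned 10-15 points from the null. A true mean close to the null would leave less room. The primary endpoint, accrual rate, is unaffected.

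The conclusion assumes that discharge coincides with the end of radiation and that the paper survey is the form printed in Appendix II, with no dated cover sheet.

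**What to change.** 1. Print two fields on the paper form: the date of the telehealth visit and the date completed.
2. Log the date on which each paper form is received.
3. Add to 7.2 that patient surveys completed before the telehealth visit, or returned by patients who had no telehealth visit, are excluded from the telehealth ratings. These patients still count towards accrual, as 7.3 provides.
4. Reconcile the paper route in 6.1 with the flowchart heading. One option is to send paper on request after the visit. Keeping the handout at discharge is workable if the dates and the rule are in place and the flowchart says so.

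The cost is two form fields, a receipt log and a sentence in the plan. A few paper surveys may be excluded, and if paper is held back until after the visit, a few returns may be lost.

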6.1.1 Study Flowchart

	Screening visit	Post-treatment visit	Sent to patient following visit
Informed consent	X		
Background information	X		
KPS	X		
Patient Satisfaction with Cancer Care Scale ^b			X
Communication assessment tool ^b			X
Health care system distrust tool ^b			X
Physician questionnaire ^a		X	
Modified physician satisfaction scale ^a		X	

- a. Physicians are to complete surveys and satisfaction scale within 2 weeks following the visit.
- b. Patients are to complete surveys within 4 weeks following the visit. They will be emailed reminders weekly following the visit.

7.0 STATISTICAL PLAN

7.1 Sample Size Determination

Accrual rate. This pilot study is designed to assess whether the accrual rate at Jefferson will be sufficient for a future noninferiority trial. For that noninferiority trial, we project that we will need to enroll a total of about 180 patients in three years, i.e., a minimum accrual rate of 5 patients per month. The enrollment duration of this pilot study will be 24 months. If the true accrual rate is 6 patients per month (i.e., 72 patients per year), then the pilot study has 83% power to establish that the accrual rate exceeds 5 patients per month (using a 1-sided test for Poisson rate, with alpha 0.05).

Patient satisfaction. The expected sample size of 60 patients will also have >90% power to establish that patient satisfaction will exceed 80%, assuming a true PSCC score of about 90% and a standard deviation of about 5% (using a one-sample t-test with alpha 0.05).

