3.0 STUDY DESIGN

3.1 General Design

This is a single arm pilot feasibility study examining a telehealth visit for the first post radiation treatment visit. Patients will be asked to fill out a questionnaire within a week of the visit. There will be no subsequent follow up per trial. The expected enrollment duration of the study is 24 months. The overall study duration is expected to be 32 months.

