3.2 Primary Study Endpoints

The primary endpoint of the study is feasibility (i.e., rate of accrual) of conducting a future randomized clinical trial comparing telehealth and in person visits

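### The planned 60–65 subjects do not fit a primary accrual test built on 24 months at 5–6 patients per month, and the exposure time is undefined if enrolment closes early

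*Combined protocol and SAP*

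**What the plan says.** Section 3.2 makes accrual the primary endpoint: "The primary endpoint of the study is feasibility (i.e., rate of accrual").

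The enrolment period is 24 months in three places: the Study Summary ("24 months for enrollment; 32 months for study duration"), section 3.1 ("The expected enrollment duration of the study is 24 months") and section 7.1, which adds the assumed rate ("The enrollment duration of this pilot study will be 24 months. If the true accrual rate is 6 patients per month (i.e., 72 patients per"). Section 7.1 derives the threshold from a future trial of about 180 patients in three years ("i.e., a minimum accrual rate of 5 patients per month"). It claims 83% power to exceed that threshold at a true 6 per month, with a one-sided Poisson test at alpha 0.05. Section 7.2 analyses monthly counts by Poisson regression but tests them against 4 per month.

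The subject numbers are on a different scale. The Study Summary gives "Number of Subjects 65". The satisfaction paragraph of section 7.1 reads "The expected sample size of 60 patients will also have >90% power".

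Section 7.3 says that withdrawn and lost subjects count towards accrual. No section says whether enrolment closes when 65 is reached, or how months after closure would enter the rate.

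**The concern.** For most endpoints, a loose fit between subject number and enrolment period is a scheduling matter. Here the endpoint is the number of patients divided by time, so the two figures together nearly fix the result. The accrual paragraph of section 7.1 implies roughly twice as many patients as the plan says it will enrol.

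The choice left open affects the main conclusion. A rate over the months actually open, a rate over a fixed 24 months with enrolment halted at 65, and a rate over 24 months with no halt are three different analyses. They have different power, and one of them cannot succeed. The choice should be fixed before accrual data are seen.

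**Working it through.** **Inputs.** Subjects: 65 (Study Summary) and 60 (7.1). Window: 24 months (Study Summary, 3.1, 7.1). Null rate: 5 per month (7.1) or 4 per month (7.2). Assumed true rate: 6 per month (7.1). One-sided alpha: 0.05 (7.1, 7.2). Counts are taken as Poisson, as in the plan.

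**1. The plan's own power figure.** Over 24 months the expected count is 5 × 24 = 120 under the null and 6 × 24 = 144 under the alternative. The smallest count c with P(X ≥ c | 120) ≤ 0.05 is 139 (probability 0.048). Power is P(X ≥ 139 | 144) = 67%. Normal approximations give 64% to 71%. The stated 83% is not reproduced. That is a separate defect and carries no weight here.

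**2. Patients implied against patients planned.** The accrual design implies 120 to 144 patients. The planned numbers imply:
- 65 / 24 = 2.71 per month
- 60 / 24 = 2.50 per month

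Both are below 4 and below 5. At a true 5 per month, the chance of 65 or fewer patients in 24 open months is about 3 in 100 million, so 65 is not a plausible outcome of the window that section 7.1 describes.

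**3. If 65 were a cap and all 24 months counted.** Rejection needs at least 139 patients against 5 per month. Against 4 per month (expected 96) it needs at least 113 (probability 0.049). A count of 65 reaches neither. Its one-sided p-value is 0.9997 against 4 per month and above 0.9999 against 5 per month.

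**4. If enrolment closes at the last planned patient and only open months count.** Expected time to 65 patients is 65 / 6 = 10.8 months or 65 / 5 = 13.0 months. These are expectations: at 5 per month there is a 26% chance that the 65th patient takes longer than 14 months.

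The time T to the nth patient is Gamma with shape n and the monthly rate. The test rejects when T falls below the 5% point of that distribution under the null. Power is the probability of this at 6 per month.

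| Null | n | Reject if nth patient arrives within | Power at 6 per month |
|---|---|---|---|
| 5 per month | 65 | 10.47 months | 40.7% |
| 5 per month | 60 | 9.57 months | 38.4% |
| 4 per month | 65 | 13.08 months | 94.6% |
| 4 per month | 60 | 11.96 months | 93.0% |

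For comparison, the full 24 months gives 67% against 5 per month and 99.7% against 4 per month.

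**The case against.** A reader might infer that the study can never pass its accrual test and must conclude that the future trial is not feasible, however fast patients enrol. The documents do not support that. It needs two rules that appear nowhere: that 65 is a hard cap, and that months after closure count as zero accrual. The Study Summary only lists a number of subjects, section 7.1 calls 60 an expected size, and section 3.1 calls 24 months an expected duration. Months when the study is closed are not naturally accrual months. Section 7.1 can also be read as a duration rule under which enrolment runs on past 65.

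A reader might also take 41% as the power of a study that stops at 65. It holds only for the 5 per month null. Against the 4 per month null that section 7.2 specifies, stopping at 65 keeps about 95%, close to the 99.7% of the full window and above the stated 83%. However, section 7.1 sets 5 per month as the minimum for the future trial, so rejecting 4 per month would not by itself show that the minimum is met.

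These points limit the consequences but do not remove the mismatch. If 65 may be exceeded, it understates expected enrolment by about half. If it may not, the 24-month window does not occur at the rates the plan assumes. Neither reading lets both figures stand, and the exposure rule is missing either way.

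**Conclusion.** The point stands as an internal inconsistency plus an undefined exposure period, both bearing on the primary endpoint. The planned 60–65 subjects are about half of the 120–144 that section 7.1 implies.

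The effect depends on the unstated rule. With a cap of 65 and all 24 months counted, neither null can be rejected. With closure at 65 and open months counted, the expected window is about 11–13 months at 5–6 per month, and power at 6 per month is about 41% or about 95% according to the null. With 24 months of unrestricted enrolment, the test is the one section 7.1 describes, but the subject number is wrong.

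These figures assume Poisson accrual at a constant rate and a true rate of 6 per month, as the plan does. Which null applies cannot be settled from the documents, because sections 7.1 and 7.2 disagree.

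**What to change.** Reconcile the subject number with the 24-month window in the Study Summary and section 7.1, and state the exposure rule in section 7.2.

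- **If 65 is a stopping number:** state that enrolment closes at the 65th patient, that exposure is the months actually open, and that months after closure are never counted as zero accrual. Replace the 24-month power statement with the power of that design under whichever null is kept once sections 7.1 and 7.2 agree: about 41% for 5 per month, about 95% for 4 per month. The cost is a wording amendment and, under the 5 per month null, a less favourable power figure.
- **If the 24-month window governs:** state that enrolment stays open throughout, give 120–144 as the expected enrolment at 5–6 per month, and describe 60–65 as only the number needed for the satisfaction estimate. This is more than wording. Section 11.1 says that the study has no funding, and roughly twice as many patients would need consent, software training and a study visit with its physician forms. The amendment should acknowledge that workload.

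The first option is the cheaper. Either should be settled before accrual data are analysed.

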7.2 Statistical Methods

The main analyses will focus on the monthly accrual rate (section 3.2). The number of patients accrued each month will be analyzed via Poisson regression. The mean (monthly rate) will be estimated and tested against the null value of 4 patients per month using a 1-sided test with alpha 0.05. In addition to accrual, we will also summarize the proportion of enrolled subjects who are lost to follow-up, since that could also impact the feasibility of the future randomized trial.

Additional analyses will focus on the secondary endpoints (section 3.3). For example, we will compute the average patient satisfaction score and test it against the null value of 75 using a one-sample t-test with alpha 0.05. We will also estimate the average patient rating of physician communication, patient distrust in the healthcare system, and physician satisfaction.

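### The 83% power stated for the primary accrual test is about 67% on section 7.1's own inputs, and section 7.2 tests against 4 per month instead of the 5 per month minimum.

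*Combined protocol and SAP*

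**What the plan says.** Section 3.2 makes the rate of accrual the primary endpoint. Section 7.1 sets the target from the future noninferiority trial: "we will need to enroll a total of about 180 patients in three years, i.e., a minimum accrual rate of 5 patients per month". For the pilot it says "The enrollment duration of this pilot study will be 24 months". It assumes a true rate of 6 per month and a one-sided test for a Poisson rate at alpha 0.05, and concludes that "the pilot study has 83% power to establish that the accrual rate exceeds 5 patients per month".

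Section 7.2 describes the analysis of the same endpoint: "The number of patients accrued each month will be analyzed via Poisson regression". The monthly rate is to be estimated and "tested against the null value of 4 patients per month using a 1-sided test with alpha 0.05". Neither section explains the move from 5 to 4.

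Two subject counts also bear on the calculation. Section 7.1 refers, for the satisfaction endpoint, to "The expected sample size of 60 patients", and the Study Summary entry for "Number of Subjects" is 65.

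**The concern.** Section 7.1 supplies every input to the power calculation, so the stated figure can be checked directly, and it looked too high for a 20% difference in rate over 24 months. It is the only operating characteristic the plan gives for its primary endpoint.

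The second problem concerns the decision itself. Section 7.1 calls 5 per month the minimum that the future trial needs. A test that rejects 4 per month does not show that this minimum is met. Two analysts, one following 7.1 and the other 7.2, could reach opposite conclusions on feasibility from the same data.

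**Working it through.** **Inputs.** From section 7.1: null rate 5 per month (180 / 36 months), true rate 6 per month, 24 months, one-sided Poisson test, alpha 0.05. From section 7.2: null rate 4 per month, one-sided, alpha 0.05. Enrolment is taken as uncapped over the 24 months.

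**Step 1: trying to reproduce 83%.** The 24-month total X is Poisson with mean 5 × 24 = 120 under the null and 6 × 24 = 144 under the alternative.

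- Exact test: take the smallest c with P(X ≥ c | 120) ≤ 0.05. P(X ≥ 138) = 0.0575 and P(X ≥ 139) = 0.0482, so c = 139 (139 / 24 = 5.79 per month). Power = P(X ≥ 139 | 144) = **0.673**.
- Score approximation: Φ[(144 − 120 − 1.645 × √120) / √144] = Φ[(24 − 18.02) / 12] = Φ(0.498) = **0.691**.
- Square-root scale: Φ[2(√144 − √120) − 1.645] = 0.672.
- Wald, variance at the alternative: Φ(24 / √144 − 1.645) = 0.639. With the variance at the null: Φ(24 / √120 − 1.645) = 0.707.
- Log rate: Φ(ln 1.2 × √144 − 1.645) = 0.706. With √120 in place of √144: 0.638.

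The one-sided methods span about 64% to 71%. None gives 83%.

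**Step 2: would another combination give 83%?**

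| Null vs true rate (per month) | Months | Exact power | Score |
|---|---|---|---|
| 5 vs 6 | 24 (as stated) | 67.3% | 69.1% |
| 5 vs 6 | 32 (overall study duration) | 77.4% | 79.0% |
| 5 vs 6 | 36 (future trial's enrolment) | 82.0% | 82.8% |
| 4 vs 6 | 24 | 99.7% | 99.6% |
| 4 vs 5 | 24 | 75.1% | 76.4% |

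The 36-month row comes closest to the stated figure. Three years is the future trial's period, not the pilot's. The documents do not say that this is where 83% came from.

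**Step 3: effect of the two nulls.** With null 4 the mean is 4 × 24 = 96. P(X ≥ 112) = 0.0595 and P(X ≥ 113) = 0.0489, so the cut-off is 113 (113 / 24 = 4.71 per month).

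A log-scale Wald test from an intercept-only Poisson regression rejects when ln(X / m₀) × √X > 1.645, where m₀ is the null mean. It gives the same cut-offs:

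- m₀ = 120: 1.642 at X = 138 and 1.733 at X = 139.
- m₀ = 96: 1.631 at X = 112 and 1.733 at X = 113.

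Totals from 113 to 138 (4.71 to 5.75 per month) therefore pass under 7.2 and fail under 7.1.

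| True rate (per month) | Pass, null 4 (≥ 113) | Pass, null 5 (≥ 139) | Opposite verdicts (113–138) |
|---|---|---|---|
| 4.5 (illustrative) | 32.8% | 0.2% | 32.5% |
| 5 | 75.1% | 4.8% | 70.2% |
| 6 | 99.7% | 67.3% | 32.4% |

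A rate of 4.5 per month would give 4.5 × 36 = 162 patients in three years, short of the 180 needed.

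**Step 4: the subject counts.** Six per month for 24 months implies 144 patients. Over 24 months, 60 patients is 2.5 per month and 65 is 2.7 per month. Both are below either null, and neither 113 nor 139 could be reached.

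**The case against.** The strongest objection is that the corrected figure is itself conditional. If enrolment stops at 60 or 65, a test on the 24-month total cannot be carried out as described, and 67% could replace one wrong number with another. This point stands as a condition: the 67% and the probabilities in Step 3 hold only if enrolment runs uncapped for 24 months. It does not rescue the 83%. Suppose enrolment stopped at 65 and the time to the 65th patient were tested, which the documents do not propose. Power at 6 per month would then be about 41% with null 5 and 95% with null 4. At 60 patients it would be about 38% and 93%.

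A second objection is that 36 months is not the only route to a figure near 83%: 4 versus 5 per month over 32 months gives 83.8% exact. That is fair. The origin is unknown, and the finding does not depend on it.

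A third is that this is an unfunded single-arm pilot, and that section 7.2 also estimates the rate, so readers can compare the estimate with 5 per month themselves. That limits the harm from the power figure. It does not settle which pass mark decides the formal test that the plan chose for its primary endpoint. The null of 4 may be deliberate, but nothing in the plan says so or relates it to the stated minimum.

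**Conclusion.** Both parts hold. On section 7.1's own inputs the power is about 67% (67.3% exact, 69.1% score, about 64% to 71% across one-sided methods), against a stated 83%. The chance of missing the criterion at 6 per month is about 33%, not 17%.

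Sections 7.1 and 7.2 set different nulls for one primary test, with pass marks of 139 and 113. The choice of section can reverse the feasibility conclusion, and under 7.2 accrual below the plan's own minimum can pass. The sizes assume Poisson counts at a constant rate and uncapped enrolment for 24 months. The conflict between the two nulls does not depend on the cap. This must be resolved before the analysis, because it fixes the primary decision rule.

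**What to change.** 1. **Settle the subject count.** State how 60 (section 7.1) and 65 (Study Summary) fit with the roughly 144 implied by 6 per month for 24 months, and whether either number is a cap. If it is, the test and its power need to be redefined for that design.
2. **Correct the power in section 7.1.** If enrolment is uncapped for 24 months, suggested text: *With a true rate of 6 per month, an exact one-sided Poisson test at alpha 0.05 has about 67% power over 24 months to show accrual above 5 per month; the criterion is met with 139 or more enrolled.*
3. **Use one null value.** Change section 7.2 to 5 per month. If the study team keeps 4, section 7.2 should justify it against the 5 per month minimum, and section 7.1 should give its power (99.7% at 6 per month, 75% at 5 per month, uncapped).

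The cost is text edits to two sections and one clarifying sentence, with no additional patients requested. The stated power becomes less favourable. Adopting null 5 in section 7.2 raises the pass mark from 113 to 139, so at a true 6 per month the pilot would miss its criterion about 33% of the time instead of 0.3%.
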